babies who suffer from even mild hypothermia are at increased risk of jaundice, sepsis, hypoglycemia [3], and death [2]; unfortunately, there are no visible signs of mild hypothermia and risks become significant long before a baby begins to feel cold to the touch. Hyperthermia is equally devastating- and sometimes can be caused by attempts to warm a baby without monitoring her temperature carefully. Additionally, large swings in temperature-known as thermal shock-can lead to negative outcomes, including death. Constant maintenance of infant temperature within a very tight range is therefore imperative [4]. Electronic temperature monitors used in high resource settings are not available in low-resource settings because they are too costly or require a constant supply of consumable thermistors. Simple digital or analog thermometers are often unavailable; when they are available, wards are often too short-staffed to permit routine monitoring at regular intervals.

Although temperature monitoring is both a critical component of neonatal care and also a well-documented challenge, there is no broad consensus on the best method to monitor temperature in low-resource settings. **We have developed a new device called NTM: a simple, affordable (\$10), and rugged tool to continuously monitor and display neonatal temperature, providing a rapid way to alert clinical staff and mothers to periods of hypo- or hyperthermia.** As shown in **Table 1**, NTM is a reusable temperature sensor attached to an infant's abdomen to detect core body temperature. It consists of a stretchy "belt" that wraps around the abdomen of the infant and senses temperature through a small stainless steel sensor. The belt and sensor can be easily cleaned between uses.

Even mild hypothermia (temperature of 36-36.5 ° C) is associated with a 1.8 fold increase in risk of mortality [2], thus our target accuracy for temperature monitoring is $\pm 0.5^{\circ}\text{C}$. We have shown that NTM meets this standard in two settings through two IRB-approved studies conducted in Houston, TX. First, we evaluated NTM's accuracy compared to a Phillips Intellivue patient monitor temperature probe in healthy adults; results show temperatures measured with NTM are within 0.3°C compared to the gold standard. A similar evaluation of NTM monitoring infants in a daycare (subjects <18 months) showed that results within 0.5°C of the gold standard.

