1. Prior to the start of the study, all study nurses/clinicians will receive training on how to use the test devices. Clinical decisions will still be based on the standard of care, which will not be interrupted during the study. The study nurse/clinician will apply the temperature sensors to the infant.
2. A research technician will be available for the duration of the study to record the data from the monitors.

Enrollment :

Enrollment will take place after fully informed and written consent from the parent or guardian. A parent will be free to withdraw their child from participating at any time, without explanation and without detriment to ongoing care. There will be no financial benefit to participants though the infants will benefit from close monitoring. A participant identification number will be assigned. This number will be used for identification purposes throughout the study.

Monitoring of Neonates:

During the trial, the following steps will be taken:

A trained study nurse will assess the subject for clinical complications before attaching the temperature monitoring device.

- 1) A trained study nurse or clinician will attach the three test temperature monitoring devices to the infant. A trained research assistant from Rice University or from the Biomedical Engineering Department at Malawi Polytechnic will observe all procedures and will notify the nurse of any observed errors so they may be corrected. They will also be able to answer any technical questions from the nurse.
- 2) The trained study nurse will attach the temperature probe from the commercial gold standard as well as provide any other care needed.
- 3) A research assistant will use a laptop to collect data from the continuous temperature monitors (NTM and gold standard). The nurse will record the temperature readings every hour from all monitors on paper forms along with the standard of care.
- 4) Each time an alarm sounds from any device (Bempu and the commercial gold standard have audible alarms), the nurse will record all temperature values including a reading taken with the standard of care method. If the subject is found to be hyper/hypothermic, the nurse will respond with the appropriate standard of care.
- 5) Temperature monitoring will continue for up to 3 days. The research assistant may ask the nurse to remove and reapply the temperature probes during this period.

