A research assistant will be available during the trial to mitigate any complications with the devices. If the subject's guardian, the nurse, or the research assistant indicates concern during the tests, temperature monitoring will be discontinued and the subject's treatment will return to the standard of care. The nurse can choose to remove one of the test devices and continue the study with the remaining monitors if any issue arises.

Clinical data will be collected on paper forms as is consistent with current clinical practice. Data from the temperature monitors will be saved on a secure study server for analysis. Clinical and/or research personnel will record information, excluding personal identifiers, on a standardized patient monitoring form. After the subject's participation is complete, a research assistant will collect and scan the form.

The following section details the variables that will be measured or calculated in the study.

Intended Data Collection:

1. Baseline demographic and relevant medical information
 - a. Recorded once at enrollment
 - i. Date of Study
 - ii. Date of Birth
 - iii. Sex
 - iv. Birth Weight
 - v. Type of delivery
 - vi. Gestational age at birth
 - vii. Corrected gestational age
 - viii. Abdominal circumference
 - ix. Admission Temperature
 - b. Recorded throughout study as clinically collected
 - i. Other comorbidities
 - ii. Medications/treatments given
 - iii. Current weight
 - iv. Additional temperature measurements taken as standard of care
2. Accuracy
 - a. Recorded automatically by study equipment
 - i. Abdominal temperature and alarms from Rice designed temperature monitor and gold standard device
 - b. Recorded every hour by study nurse or as alarm events occur
 - i. Temperature measurements from other devices
 - ii. Temperature measurements using standard of care method (axillary)
 - iii. Ambient temperature
 - iv. Current thermal treatment, if any
 - c. Movement/other caregiving
 - d. Fit/tightness of the devices

A log of observed user error and comments may be used to improve the usability of the test devices.

[vii] Data Management and Analysis

Personal identifiers will be removed from the data which will be kept on a secure server accessible only to study personnel.

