The accuracy of the temperature sensors will be determined by calculating the difference between the temperatures recorded by the temperature sensor and the commercial patient monitor at each point in time. The average error between the temperature sensor and the gold standard will be calculated for each subject and compiled in a Bland-Altman plot. The 95% limits of agreement will be calculated. Our target error is less than +/- 0.5 C.

For the devices that do not provide a continuous numerical reading, the recorded state every hour will be compared to the gold standard at that point in time. The sensitivity and specificity for hypo/hyperthermia will be calculated for each device.

The ability of each device to accurately diagnose hypothermia will also be calculated with respect to the alarm events for each device for which they were recorded. The sensitivity and specificity will be determined using the number of false alarms collected during the study.

As a secondary analysis, the errors will be plotted against thermal treatment type and ambient temperature to determine their confounding effects on accuracy. An ANOVA will be used to determine statistical significance.

The research team from Rice University and QECH will be responsible for all data analysis. We plan to analyze data using Excel, MATLAB, and associated statistics packages.

[viii] Results Presentation

Statistical analysis will be performed and means, limits of agreement, sensitivities and specificities will be reported. Tables and graphs may also be used to present any additional correlations, explain outliers, or demonstrate confounding effects.

[ix] Dissemination of Results

The results of this study will be made available to the Ministry of Health, COMREC, the College of Medicine Library, the Department of Paediatrics, and other partners working in neonatal and child health. A copy of the final report and any published papers or abstracts will be submitted to The Health Sciences Research Committee and the University Research and Publication Committee (URPC) through the COMREC Secretariat. Findings will be published in academic journals and conference

proceedings in an effort to disseminate results to potential end-users. The research findings of this study will be critical in the evaluation of future interventions.

I. Ethical considerations

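### The planned analysis cannot show whether NTM alerts late or misses episodes: averaging within infant cancels response lag, and alarm sensitivity is to come from a count of false alarms

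*Combined protocol and SAP*

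**What the plan says.** Section H [vii] sets out three analyses that bear on NTM.

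- **Numerical accuracy.** This is found by "calculating the difference between the temperatures recorded by the temperature sensor and the commercial patient monitor at each point in time". Then: "The average error between the temperature sensor and the gold standard will be calculated for each subject and compiled in a Bland-Altman plot". On the spread of these errors the plan adds: "The 95% limits of agreement will be calculated", without saying whether from infant means or single readings. "Our target error is less than +/- 0.5 C", without saying whether this applies to the mean, the limits or each reading.
- **Classification.** "The sensitivity and specificity for hypo/hyperthermia will be calculated for each device". I read this as including NTM.
- **Alarm events.** Each device's ability to diagnose hypothermia is assessed on its recorded alarm events, with sensitivity and specificity worked out from the number of false alarms.

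Section E gives the aim of evaluating how well the three devices detect hypo- and hyperthermia, and objective 1c (section G) covers temperature during alarm events. Section E also describes NTM as "providing a rapid way to alert clinical staff and mothers to periods of hypo- or hyperthermia". Its alert is a light that flashes below 36.5 °C or above 37.5 °C.

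Section H [vi], Intended Data Collection, item 2a, lists as recorded automatically: "Abdominal temperature and alarms from Rice designed temperature monitor and gold standard device". The nurse's alarm record (H [vi], Monitoring of Neonates, step 4) is made when an alarm sounds, and only Bempu and the gold standard are named as audible.

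No section defines an episode, a missed alert, a response lag, a time to alert, or a window for matching an NTM alert to a gold-standard episode.

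**The concern.** A sensor that responds slowly reads too warm while an infant cools and too cold while it rewarms. Within an infant these errors have opposite signs and largely cancel, so the planned mean error can be near zero for a fast device and a slow one alike. The practical difference between them is when, and whether, the light flashes after the infant crosses a threshold.

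The alarm-event analysis is where this should be seen, but false alarms concern alerts that were given, not episodes that went without one. The study could report NTM as within ±0.5 °C without being able to say what share of hypothermic episodes it flagged, or how late. Those are central results for a monitor meant to detect hypo- and hyperthermia.

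**Working it through.** The plan states no lag, response time or delay, so it has no figure of its own to reproduce.

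**1. Lag and the mean error.** For a pure lag L over monitoring time T, mean error ≈ −L × (net temperature change) ÷ T. T = 72 h is the plan's maximum of 3 days; L = 0.5 h and a net change of 1 °C are assumed. Size: 0.5 × 1 ÷ 72 = 0.007 °C. During a steady fall of 1 °C/h the same lag gives an error of 0.5 × 1 = 0.5 °C.

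**2. False alarms and sensitivity.** Sensitivity = TP ÷ (TP + FN). The false-alarm count is FP, which does not appear. Specificity = TN ÷ (TN + FP) also needs TN, hence a defined unit without an episode. With A alerts in total, FP gives only (A − FP) ÷ A, the positive predictive value.

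**3. Single episodes.** Assume NTM follows the true temperature with time constant τ and no other error, from a baseline of 36.9 °C, so an alert needs a fall of 0.4 °C.

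- *Fall of 1.0 °C over 30 min.* The gold standard crosses at 0.4 × 30 = 12 min. NTM crosses when [t − τ(1 − e^(−t/τ))] ÷ 30 = 0.4. For τ = 10 min, t = 20.7 and the delay is 8.7 min. For τ = 20 min, t = 26.7 and the delay is 14.7 min.
- *Fall of 0.6 °C over 15 min, 5-min hold, 15-min recovery.* The rate is 0.6 ÷ 15 = 0.04 °C/min. The infant is below 36.5 °C for 5 + 5 + 5 = 15 min. For τ = 30 min, NTM's fall is 0.04 × [15 − 30(1 − e^(−0.5))] = 0.128 °C at the end of the ramp and 0.6 − (0.6 − 0.128) × e^(−5/30) = 0.200 °C after the hold. It peaks s = 30 × ln(1.6 ÷ 1.2) = 8.6 min into recovery, at 0.6 − 0.04 × 8.6 = 0.26 °C. That is short of 0.4 °C, so NTM never alerts.

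**4. Limits from single readings.** Assumed: 60 infants, 72 h, six cooling episodes each, lag the only error. Limits from infant means stayed within ±0.001 °C throughout. Single-reading limits (°C) were:

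| Episode (depth; ramp; hold) | τ 20 min | τ 30 min | τ 60 min |
|---|---|---|---|
| 0.6 °C; 15 min; 5 min | ±0.13 | ±0.14 | ±0.16 |
| 1.0 °C; 30 min; 30 min | ±0.25 | ±0.31 | ±0.39 |
| 1.5 °C; 30 min; 60 min | ±0.39 | ±0.49 | ±0.65 |

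Only the longest lag with the largest swings breaches ±0.5 °C.

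**5. Delay and misses with other errors present.** Assumed: 60 infants × 72 h, smooth temperature with mean 36.9 and SD 0.4 °C, between-infant offset SD 0.08, noise SD 0.08. Temperature smoothness and alert rule were varied.

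| τ (min) | Median alert delay (min) | Episodes ≥ 15 min missed |
|---|---|---|
| 0 | 0–1 | 2–3% |
| 10 | 5–9 | 1–5% |
| 30 | 24–28 | 4–16% |
| 60 | 44–47 | 11–34% |

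Limits from infant means were about ±0.15 °C at every τ. If one noisy minute counts as an alert, the τ = 60 figures shrink to 22–30 min and 4–17%.

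**6. The planned classification.** Under similar assumptions, sensitivity below 36.5 °C at τ = 0, 30 and 60 min was about 0.89, 0.65 and 0.49, or 0.87, 0.78 and 0.69, depending on smoothness. It responds to lag but is not in units of time. A fixed offset lowers it too: in one setting hourly sensitivity was 0.71 with a 30-min lag and 0.72 with no lag but a +0.08 °C offset.

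**The case against.** A reader might infer that NTM is judged only on same-instant differences, so that a slow device would pass unnoticed. The documents do not support that. Sensitivity and specificity are planned for each device, an alarm-event analysis is planned, and when the gold standard sounds the nurse records all devices' values. A long lag would visibly lower sensitivity. A large fixed offset would also appear in the mean error, so near-zero bias with poor sensitivity would point away from simple miscalibration. These points stand, and they narrow the concern to what the planned outputs cannot give: the delay, and late as distinct from missed.

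The nurse's record at the gold-standard alarm does not fill that gap. In the 1.0 °C episodes of step 4, at the instant the gold standard crossed 36.5 °C, NTM was alerting in 0 of 360 episodes with τ = 2 min and in 0 of 360 with τ = 30 min. A reading taken then cannot tell a 2-minute delay from a 19-minute one.

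It is also fair that the documents give no sign that NTM is slow. At τ = 10 min the effect on sensitivity is small, and missed-episode figures move with the assumed smoothness and alert rule. Rapid alerting is background text in section E, not an objective, and this is a pilot. Not measuring speed is therefore a gap in scope rather than a broken objective. The false-alarm rule is different: it is a planned analysis that cannot produce the sensitivity it promises, whatever NTM's speed.

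**Conclusion.** The concern holds in limited form. Averaging within infant removes lag from the headline accuracy result, and the alarm rule cannot show missed or late alerts. The planned classification would register a long lag but would not measure it. The detection aim and objective 1c are therefore only partly answered, although the data needed are to be logged automatically.

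The cancellation and the failure of the false-alarm rule follow from the definitions. The delay and missed-episode figures do not: they rest on assumed response times, temperature patterns and alert rules, and should be read as ranges. They should not be taken as evidence that NTM is slow. This is a worthwhile and cheap improvement, not a flaw that invalidates the accuracy comparison.

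**What to change.** In H [vii], replace the false-alarm rule with an episode-level analysis of the automatic logs:

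- Define a gold-standard episode in advance, as below 36.5 °C or above 37.5 °C (NTM's own alert thresholds in section E) for a pre-set minimum time, and a window for matching NTM alerts to it.
- Report the share of episodes to which NTM alerted (sensitivity), the share of NTM alerts with no gold-standard episode (false alarms), and the delay from gold-standard crossing to NTM alert.
- Treat infants as clusters in the intervals.
- State that NTM alerts come from the automatic log, since its alert is a light and the nurse's record is triggered by alarms that sound.

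A cross-correlation estimate of lag beside the limits of agreement is optional.

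The cost is a paragraph of text and some programming, with no new patients or extra measurements on infants. Two things must be settled first. The episode length and window are judgements to fix before the data are seen. The NTM and gold-standard logs must also be time-aligned, which no section currently states.

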Specific objectives: In this study, we intend to evaluate the accuracy of these devices at Queen Elizabeth Central Hospital (QECH) by comparing the temperature readings to a commercially available gold standard device. We also want to ensure the devices are easy to understand and use and could be implemented in the wards.

The specific objectives are:

1. To determine the accuracy of the NTM, Bempu, and ThermoSpot devices when used by nurses in the neonatal ward by comparing
 - a. Continuous temperature measurements
 - b. Periodic temperature measurements
 - c. Temperature during alarm events
2. To ensure the NTM is easy to understand and use in the
 - a. Nursery with open cots, hot cots, and radiant warmers
 - b. KMC ward

Methodology: This is a method comparison study taking place in the neonatal ward (Chatinkha) and KMC ward at Queen Elizabeth Central Hospital (QECH). Up to 60 infants in need of temperature monitoring or thermal care will be enrolled in the study. The infants will be continuously monitored using the NTM, Bempu, ThermoSpot, and a gold standard temperature monitor for up to 3 days. The accuracy of the devices will be determined by calculating the difference between the temperatures recorded by the test devices and the commercial patient monitor at each point in time. Our target error is less than +/- 0.5 C.

Implications of the study and dissemination plans: The data collected here will be used to evaluate the use of the temperature monitoring devices as tools for monitoring and diagnosing hypothermia. The results of this study will be made available to our partners working in neonatal and child health. Findings will be published in academic journals and conference proceedings in an effort to disseminate results to potential end-users.

E. Background Information and Introduction

Neonatal hypothermia is a pervasive global challenge; as many as 85% of infants born in hospitals in low-resource settings are too cold (defined as a temperature <36.5C) [1]. A recent study of 23,240 newborns in Nepal showed that babies with moderate hypothermia are nearly five times more likely to die than normothermic infants; the risk of death is more than 23 times higher for babies with severe hypothermia [2].

While the risks of being too cold are well recognized, hypothermia remains a largely invisible problem in overcrowded newborn units in low-resource settings. Data show that

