The user interface of the device was designed with feedback from Malawian doctors and nurses. The baby's temperature is displayed continuously on the battery powered control box; if the infant's temperature drops below 36.5°C , a blue light atop the box flashes to signal that intervention is necessary. Similarly, if the infant's temperature exceeds 37.5°C , a red light flashes signaling for intervention. The light flashes speed up with degree of hypo- or hyperthermia.

NTM has important advantages compared to two other approaches which have been developed to address this need (Table 1). Unlike Bempu, a wrist-worn monitor that provides an audible alarm, NTM is placed over the liver to measure core temperature and it displays temperature continuously. Neonatal nurses on our development team identified

Table 1: Options for low cost neonatal temperature monitoring

	NTM	Bempu	ThermoSpot
Benefits	Easy to understand continuous visual cues and digital temperature display, no disposables	Audiovisual alarm, intuitive, also suitable for in home use	Visual cue for different levels of hypothermia, low cost, no power required
Cost	\$10	\$30 (2000 Rs) Bempu.com	\$0.50 Maternova.net

temperatures above 36.5°C, brown between 35.5 and 36.4°C, and black below 35.5°C) it is not reusable and the color change can go unnoticed without scheduled monitoring.

In this study we plan to evaluate the ability of NTM, Bempu, and ThermoSpot to detect hypo- and hyperthermia in neonates by comparing to a gold standard electronic temperature monitor used in high-resource settings.

F. Rationale/Justification for the research project

Together, prematurity and infection account for more than 50% of neonatal mortality globally, resulting in a combined 1.7 million deaths each year [5]. Improved ability to monitor neonatal temperature could help improve outcomes for both preterm babies, who are at high risk of hypothermia, as well as babies with infections, who are at high risk of hyperthermia. In many low-resource settings, routine monitoring is simply not possible due to staff and equipment shortages. Our innovation, NTM, offers an affordable, rugged, low-power tool that provides constant monitoring with digital display of temperature and a simple light to notify a guardian or nurse when intervention is necessary. Furthermore, NTM is reusable, requires no consumables, and has a very simple design to facilitate easy maintenance and repairs.

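### Limits of agreement taken from one mean error per infant understate single-reading error, so NTM can appear to meet ±0.5 °C when its readings do not

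*Combined protocol and SAP*

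**What the plan says.** H [vii] (Data Management and Analysis) begins with the sensor-minus-monitor difference at each time point. It then says: "The average error between the temperature sensor and the gold standard will be calculated for each subject and compiled in a Bland-Altman plot". Directly after that comes: "The 95% limits of agreement will be calculated. Our target error is less than +/- 0.5 C". The limits sentence names no data set, variance formula or repeated-measures method, and the text does not say which quantity must meet the target.

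Other sections bear on the unit:

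- **D, Methodology:** accuracy is obtained by "calculating the difference between the temperatures recorded by the test devices and the commercial patient monitor at each point in time". The target follows, and averaging within infants is not mentioned.
- **E, Background:** the target is derived from the mortality risk of mild hypothermia ("thus our target accuracy for temperature monitoring is" ±0.5 °C). Below 36.5 °C, "a blue light atop the box flashes to signal that intervention is necessary"; a red light does the same above 37.5 °C.
- **H [vi], Monitoring of Neonates, steps 3 and 5:** readings are written down hourly, and NTM and the gold standard are also logged by laptop. "Temperature monitoring will continue for up to 3 days", and "The research assistant may ask the nurse to remove and reapply the temperature probes during this period".

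H [vii] also plans a classification analysis: "The sensitivity and specificity for hypo/hyperthermia will be calculated for each device".

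**The concern.** A nurse or mother sees the current reading, not a three-day average, so the relevant question is how far one reading may lie from the gold standard. Limits built from infant means answer a different question, namely how consistent the average offset is from one infant to the next.

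An offset that persists throughout an infant's monitoring survives averaging. Error that fluctuates within an infant largely does not, and the plan itself expects such error: probes may be reapplied, and H [vi] records movement, fit, thermal treatment and ambient temperature. Infant-mean limits therefore err towards being too narrow, which favours the device.

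The issue concerns NTM, the test device with a continuous numerical reading. Accuracy is the first specific objective, limits of agreement are a named result in H [viii], and ±0.5 °C is the plan's only numerical accuracy target. What is at stake is a published agreement estimate that places NTM within target when its single readings are not.

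**Working it through.** **Inputs from the documents.** Target ±0.5 °C (E; H [vii]); up to 60 infants, 30 per ward (H [v]); up to 3 days of hourly readings (H [vi]), hence at most 3 × 24 = 72 hourly pairs per infant. The sample size has no SD or precision calculation behind it, so there is no planned figure to reproduce.

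**Assumed inputs.** The documents give no SD for the error, so the between-infant SD (sb), within-infant SD (sw) and hourly autocorrelation (ρ) are assumptions, varied below. Bias is zero unless stated.

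**Formulas.** For half-widths of the 95% limits:

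- from infant means: 1.96 × √(sb² + sw²/n_eff)
- from single readings: 1.96 × √(sb² + sw²)
- share of readings off by more than 0.5 °C: 2 × [1 − Φ(0.5/√(sb² + sw²))]
- under first-order autocorrelation: n_eff = n / [1 + 2 Σ (1 − k/n) ρ^k], k = 1 to n − 1

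Whenever sw > 0 and n_eff > 1, the first half-width is smaller than the second. The direction therefore needs no assumed value. With zero bias, limits inside ±0.5 °C need an SD of at most 0.5/1.96 = 0.255 °C.

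**Central case: sb = 0.15, sw = 0.30, n = 72.**

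- Single readings: √(0.0225 + 0.0900) = 0.335; × 1.96 = ±0.66 °C, outside the target. Share off by more than 0.5 °C: 2 × [1 − Φ(0.5/0.335)] = 13.6%.
- Infant means, independent readings: √(0.0225 + 0.0900/72) = 0.154; × 1.96 = ±0.30 °C, inside the target.

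| ρ | n_eff (n = 72) | Infant-mean limits, central case | Infant-mean limits over the 9-pair grid | Pairs where infant means pass and single readings fail |
|---|---|---|---|---|
| 0 | 72 | ±0.30 | ±0.20 to ±0.40 | 7 of 9 |
| 0.8 | 8.5 | ±0.36 | ±0.24 to ±0.48 | 7 of 9 |
| 0.9 | 4.4 | ±0.41 | ±0.27 to ±0.54 | 6 of 9 |
| 0.95 | 2.5 | ±0.47 | ±0.32 to ±0.63 | 3 of 9 |

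The grid crosses sb = 0.10, 0.15, 0.20 with sw = 0.20, 0.30, 0.40. Single-reading limits over it run from ±0.44 to ±0.88 °C whatever ρ is.

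**Where the two agree.**

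- Both pass at sb/sw = 0.10/0.20 (single readings ±0.44) and 0.15/0.20 (±0.49).
- Both fail at 0.20/0.40 with ρ = 0.9 (±0.54 against ±0.88).
- Both fail in the central case with only 24 hourly pairs and ρ = 0.9 (n_eff 2.0; ±0.51 against ±0.66).
- In the central case with independent readings, a bias above 0.5 − 0.302 = 0.198 °C takes the infant-mean limit past 0.5 as well.

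**Simulation of the central case** (60 infants × 72 pairs, 1000 replicates). Mean half-widths were 0.300 from infant means, 0.656 from naive pooling of all readings and 0.657 from variance components. At ρ = 0.9 they were 0.405, 0.654 and 0.656. Pooling thus gives about the right width with balanced data, whereas infant means do not.

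**The case against.** The strongest reply is that the text is ambiguous rather than wrong. The limits sentence names no unit, the paragraph opens with time-point differences, and the executive summary sets the target beside those differences without mentioning averages or limits. If the limits were meant to pool all readings, their width would be about right. That reading is possible, but the only data named for the Bland-Altman plot are infant averages and the limits follow directly. Even on the pooled reading, H [vii] must say so, and any confidence interval must allow for clustering.

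Other planned analyses might expose large single errors. Sensitivity and specificity would show misclassification at the thresholds, and the plots of error against thermal treatment and ambient temperature might be at reading level, though the plan does not say. Neither supplies single-reading limits or tests ±0.5 °C.

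The sizes are assumed. That stands. The count of 7 in 9 depends on starting sw at 0.20; adding sw = 0.10 at the same three sb values gives single-reading limits of ±0.28, ±0.35 and ±0.44, all passing, so 7 of 12 with independent readings. Section E reports NTM within 0.3 °C in adults and 0.5 °C in daycare infants, but does not define 'within' and concerns other populations, so it neither anchors nor refutes the central case.

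Finally, this is a pilot with no formal pass/fail rule, test devices do not guide care, and the paired data are kept, so the limits could be recalculated later. All true. This confines the harm to a misleading reported result; it does not make the described analysis suitable.

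**Conclusion.** The concern holds. Followed in order, H [vii] yields limits for an infant's mean error, while the plan's own account of accuracy and of how NTM is used concerns the single reading. No section plans limits that include within-infant variance. That the infant-mean limits are narrower is algebraic; by how much, and whether the comparison with ±0.5 °C reverses, depends on SDs, autocorrelation, number of pairs and bias that the documents do not give. Under plausible assumed values the understatement can be more than twofold, and reversal is common but not universal. The text needs correcting before analysis because the error affects the main agreement result for the first objective and runs in the device's favour.

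**What to change.** In H [vii]:

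1. Calculate NTM limits of agreement from all paired NTM and gold-standard differences with infant as a random effect: mean bias ± 1.96 × √(between-infant variance + within-infant variance).
2. Give confidence intervals that respect clustering by infant, for example from a bootstrap that resamples infants.
3. State that ±0.5 °C is judged against these single-reading limits, and report the percentage of readings within ±0.5 °C.
4. Keep the plot of per-infant means only as a description of bias, labelled as such.

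The cost is a few sentences and slightly more analysis of data already to be collected, with no change to design or sample size. The downside is wider, less favourable limits.
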